6.0 STUDY INTERVENTIONS

6.1 Description of study groups

There will be two arms or groups in this study

1. **(Standard of Care: SC)** - follow institutional ICU management algorithm for septic shock
2. **(Early metabolic resuscitation with Standard of Care: SC + EMR)** - infusion of EMR solution with Standard of Care

6.2 Description of EMR protocol group

The combined EMR solution will be infused at a set rate (<12hours or > 12 hours) as the main metabolic resuscitation strategy. Additional volume may be required to achieve euvoolemia. This will be in the form of either albumin (if serum albumin < 3 as mentioned below) or crystalloids depending on the clinical situation and the serum sodium content.

The early metabolic support components include the following:

Table 2 show the components of the EMR solutions per liter

Table 2. EMR Solution

EMR SOLUTION WILL BE PREPARED IN A BAG WITH THE FOLLOWING COMPONENTS	
EMR I (with potassium)	EMR II * (without potassium)
Dextrose 50% with Potassium Phosphate 30 mmol	Dextrose 50% with Sodium Phosphate 30 mmol
Sodium Acetate 75 mEq	Sodium Acetate 55 mEq
Sodium Chloride 75 mEq	Sodium Chloride 55 mEq
Thiamine 500 mg	Thiamine 500 mg
Folic Acid 1 mg	Folic Acid 1 mg
Zinc Sulfate 5 mg	Zinc Sulfate 5 mg
Selenium 60 mcg	Selenium 60 mcg
Copper 1.2 mg	Copper 1.2 mg
Chromium 12 mcg	Chromium 12 mcg
Magnesium Sulfate 16 mEq	Magnesium Sulfate 16 mEq
Multivitamin for Injection 10 ml	Multivitamin for Injection 10 ml

Insulin 25 units (actrapid)	Insulin 25 units (actrapid)
SPECIFICATIONS OF THE TREATMENT AND ADJUVANTS	

A. EMR solutions: will be infused at 0.5 ml/kg/h by CVC. If serum glucose is greater than 180mg/dL-250mg/dL, EMR solution will be infused at 0.25 ml/kg/h. Prior to starting EMR infusion, a bolus of 500mg IV of thiamine should be administered to all patients on SC+EMR arm of treatment.
 
B. Clinisol 15% AA. Infusion rate (IV) will be 0.25 ml/kg/hr for the first 12 hours, then 0.5 ml/kg/h for the remainder of the intervention – this must be infused via a dedicated Central Venous Catheter.
 
C. If serum albumin is lower than 3 g/dL, then use Albumin 25% 100ml IV Q 8 hours until serum albumin level \geq 3 g/dL – this can be infused peripherally or centrally. Once albumin >3g/dL this can be stopped, but should resume whenever albumin falls <3g/dL
 
D. Vitamin C 1g q 8h IV (100 ml per gram of Vitamin C)
	

**If the level of K is \geq 5.0mmol/L the patient will receive EMR II. Any conditions, which the K⁺ trend is rising, clinicians could opt to switch EMR solution to prevent hyperkalemia.*

This solution does not contain potassium phosphate, but contains sodium phosphate. Sodium content is consequently adjusted to have a compatible concentration

Total amount of administered fluids on day one.

EMR I or II formula during first 12 hours: **EMR** 0.5 ml/kg/h + **Clinisol** 0.25 ml/kg/h + **Vitamin C** 100 ml q8. **EMR + Clinisol:** 0.75 ml/kg/h in a 70 kg individual will be 630 mL/12 hr + (100 ml VitC x 1 times).

TOTAL= 730 mL within the first 12h of treatment

EMR I or II formula after 12 hours: **EMR** 0.5 ml/kg/h + **Clinisol** 0.5 ml/kg/h + **Vitamin C** 100ml q8. **EMR + Clinisol =** 1ml/kg/h in a 70 kg individual will be 840 mL/12hr + (100ml VitC x 3 times)

TOTAL = 1.98 L/24h

For SC+ EMR Arm – Serum targets:

- a. Target serum Albumin > 3 g/dl
- b. Target serum Magnesium of 3mg/dl

Sodium management

- a. <130 meq/L use Sodium Chloride 0.90% and call the PI
- b. 130-134 meq/L use Plasmalyte
- c. 135-140 meq/L Ringer's Lactate
- d. >140 meq/L use Sodium Chloride 0.45%

6.3 Duration of intervention

The above infusions will be started and continued for seven days unless the patient dies or is discharged from the ICU. Infusions have to be continuously maintained and not stopped for any routine investigations. If the patient is tolerating enteral tube feeds at $\geq 70\%$ of goal for a full 24 hours as determined by the ICU dietician, the intervention will be stopped (established weaning process to avoid precipitation of hypoglycemia).

6.4 Adherence Assessment

Adherence will be defined as continuous infusion of study solutions 90% of the time from onset of study until cessation. This will be assessed via the electronic patient record, which will record infusion stop/start times.

Patients who have requested to be withdrawn from the study or achieve Comfort Care status during ICU stay will be removed from the study. Those who die or begin renal replacement will be followed up but the interventions will be stopped.

[figure not shown]

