1.0 STUDY OBJECTIVES

1.1 Primary Objective:

To assess the efficacy of administering Early Metabolic Resuscitation with Standard of Care (SC + EMR) in patients diagnosed with septic shock for reducing 28-day mortality versus using the Standard of Care alone (SC). Twenty-eight day mortality is defined during the time from the day SC+EMR or SC was first administered until a patient dies or is followed through 28 days (whichever comes first).

1.2 Secondary Objectives:

1. To assess whether Early Metabolic Resuscitation with standard of care (SC + EMR) is an effective strategy to reduce ICU mortality, hospital mortality, and 90-day mortality of septic shock patients relative to SC. ICU mortality is defined as mortality at ICU discharge relative to SC.
2. To compare the time to death from any cause between patients administered SC + EMR versus SC after being diagnosed with septic shock.
3. To assess whether SC + EMR is an effective strategy to reduce complications of septic shock such as: i) acute kidney injury, ii) dialysis requirements, iii) need for cardiovascular support or days on vasopressors, iv) need for invasive ventilation, days on ventilator support, v) duration of ICU stay, and vi) duration of hospital stay versus SC.
4. To describe the presence of any adverse effects between the two study groups (SC + EMR group vs SC group); thus, characterizing their safety.

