5.2 Exclusion Criteria

- Do Not Resuscitate (DNR),
- Comfort Care and end-of-life patients
- Patients with SOFA score greater than 12
- Pregnant women
- Jehovah witnesses that do not accept albumin.
- Active bleeding (e.g., gastrointestinal bleeding)
- Acute neurological syndromes (e.g., stroke, hemorrhage, etc)
- End-stage Renal Disease (ESRD)
- Transaminitis

- Renal replacement therapy
- Chronic Liver Disease
 - Childs-Pugh Class C or
 - Diagnosis of Cirrhosis
- Heart rate less than 50 bpm,
- Respiratory rate less than 8 rpm,
- Temperature less than 95°F or 35°C
- Tumor Lysis Syndrome
- Myasthenia gravis
- Sulfite Allergy: amino acids administration are contraindicated. It is more common in steroid dependent asthmatics. (Please note that this is NOT sulfa allergy and is NOT contraindicated patients with sulfa allergy). Sulfites are present in dried fruits, beer, wines, sausages, jams, maple syrup, and many other food products.
- Serum sodium concentration < 130 mEq/L or >150 mEq/L (Note: Once serum sodium levels are \geq 130 or \leq 150 mEq/L within 12 hours after meeting inclusion criteria, the patient can then be considered for the study. This is only a temporary restriction).
- Serum Creatinine level: SCr \geq 3 mg/dL (Note: Once serum creatinine levels are \leq 2.5 mg/dL within 12 hours after meeting inclusion criteria, the patient can then be considered for the study. This is only a temporary restriction).
- Urine output < 400 cc/24hrs (Note: Once urine output levels are \geq 400 cc within 12 hours after meeting inclusion criteria, the patient can then be considered for the study. This is only a temporary restriction).
- Hyperkalemia K > 5.5 mEq/L (Note: Once potassium levels are \leq 5.5 mEq/L within 12 hours after meeting inclusion criteria, the patient can then be considered for the study. This is only a temporary restriction).
- Hyperglycemia: Glucose > 250 mg/dL (Note: Once glucose is below 250 mg/dL within 12 hours after meeting inclusion criteria, the patient can then be considered for the study. This is only a temporary restriction.)

- Hypophosphatemia: Serum Phosphorous < 1.5 mg/dL (Note: Once phosphorus is above 1.5 mg/dL within 12 hours after meeting inclusion criteria, the patient can then be considered for the study. This is only a temporary restriction.)

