7.2 Data to be collected prospectively

Vital signs including blood pressure, heart rate, respiratory rate, pulse oximetry, co-oximetry will be measured, as well as cardiac assessment by 2D echocardiogram. The following information will be collected prospectively if available. The order sets describe the timing and frequency of the lab draws. If clinical condition indicates, blood tests may occur more frequently at discretion of primary team. Additional tests may not necessarily be recorded. The below order sets indicate minimum frequency. *Day 0 is day of recruitment.*

Daily SOFA scores - will be generated automatically by the electronic health record if this option exists in the institution or manually with table 1 once daily.

Laboratory Data:

1. Complete Blood Count and Coagulation profile
 - a. First 24hrs after start of intervention: every 8 hours ± 120 minutes
 - b. After 24hrs of intervention: every 12 hours ± 120 minutes
2. Cultures (as ordered by primary team – *we will not specify culture requirements though at least one set of blood cultures should be taken as required by sepsis management algorithm*)
3. Liver function tests and lipase
 - a. First 24hrs after start of intervention: every 12 hours ± 120 minutes
 - b. After 24hrs of intervention: every 24 hours ± 120 minutes
4. Serum cholesterol (to be collected once daily only days 1, 3, 5)
5. Thyroid test: Thyroid function tests (to be collected once daily only days 1, 3, 5)
6. Blood chemistry panel
 - a. Includes: Albumin, BUN, Ca^{2+} , Na^+ , K^+ , Cl^- , CO_2 , Creatinine, Glucose, Phosphorus, and Gama-Glutamyl transpeptidase
 - b. First 24-hrs after start of intervention: every 4 hours ± 120 minutes (Will require VAMP System or similar blood sparing device to avoid wasting blood)
 - c. After 24-hrs of intervention: every 8 hours ± 120 minutes
7. Arterial blood gas and venous blood gas (via central venous catheter)

- a. First 24hrs after start of intervention: every 4 hours ± 120 minutes
- b. After 24hrs of intervention: every 8 hours ± 120 minutes

8. Lactic acid

- a. First 24-hrs after start of intervention: every 4 hours ± 120 minutes
- b. After 24-hrs of intervention: every 8 hours ± 120 minutes

9. Serum Cortisol once daily (morning)

10. Uric acid once daily (morning)

11. Inflammatory markers (ESR, Procalcitonin) to be collected once daily.

12. Creatinine phosphokinase (to be collected once daily only on day 1, 3, 5)

Outcome data:

- 1. Length of stay (LOS)

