 - a. Time from hospital admission to admission to the ICU (Length of stay before admission to the ICU)
 - b. Length of the stay in the ICU
 - c. Length of hospital stay
- 2. Mortality
 - a. Hospital mortality
 - b. ICU mortality
 - c. 28 day mortality
 - d. 90 day mortality
- 3. Ventilator days – ventilator free days, duration of intubation (days)
- 4. Any newly documented hospital acquired infection(s)
- 5. Any acute kidney injury as defined by acute kidney injury network criteria:
 - a. An acute (within 48h) rise in serum creatinine of 0.3g/dl or more

- b. A percentage increase of serum creatinine of 50% or more
 - c. Documented oliguria <0.5 ml/kg/hr for >6 hours
 - d. Need for dialysis
 - e. Dialysis free days
- 6. Inotropic free days and duration of inotropic support (hours or days)
- 7. Vital signs and any hemodynamic monitoring (cardiac index, CVP, ScvO2) implemented will be recorded – there is no specific requirement for hemodynamic monitoring beyond arterial-line recorded MAP/BP/HR.
- 8. All patients will be followed up for up to 90 days.

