9.0 CRITERIA FOR INTERVENTION DISCONTINUATION

These include:

- Patient's consent withdrawn
- Patient's discharge from the ICU
- Allergy to any of the components of EMR
- Patient requiring renal replacement therapy
- Patient's death
- Patient changed to Comfort Care status
- Patients receiving greater than 70% of their nutritional needs via enteral nutrition
- Unable to undergo placement of CVC for any technical reasons or withdrawal of CVC
- Severe fluid overload or electrolyte abnormality requiring discontinuation (as described in Chapter 7)
- Jehovah's Witness who decides not to accept albumin.
- If patient develops a known contraindication, or an unspecified condition where the clinician thinks the patient should be taken off the protocol, then there should be a discussion and treatment should be weaned according to safety protocol.

In case of discontinuation, please follow weaning procedure detailed in section 6.7.

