10.5 Data Analyses

Descriptive statistics including the mean, standard deviation, median, and range will be used to summarize continuous variables. Frequency counts and percentages will be used to summarize categorical variables. Categorical variables, including 28 day mortality, will be compared between intervention groups using a chi-square test, or Fisher's exact tests if more appropriate. Continuous variables will be compared between intervention groups using an independent samples t-test, or Wilcoxon rank-sum test if more appropriate.

Logistic regression will be used to assess relationships between patient characteristics and binary study outcomes of interest. Continuous variables, including the time on cardiovascular support and time on ventilator, will be compared using t-tests or Wilcoxon rank-sum tests.

Time to event analyses will be conducted using Cox proportional hazards regression. For 28-day mortality, living patients will be censored after one month after the treatment was given. For overall survival, patients will be followed until time of death or date of last follow-up (maximum 6 months). Kaplan-Meier plots will be used to visually compare time to death from any cause between intervention arms followed by a log-rank test to compare survival distributions.

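### Section 6.4 removes patients who reach Comfort Care in the ICU from the study, in conflict with the 28-day mortality endpoint, and no analysis population is stated that would keep their deaths in the primary comparison

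*Combined protocol and SAP*

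**What the plan says.** Section 6.4 (Adherence Assessment) contains two adjoining rules. The first is "Patients who have requested to be withdrawn from the study or achieve Comfort Care status during ICU stay will be removed from the study". The second is "Those who die or begin renal replacement will be followed up but the interventions will be stopped".

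The primary endpoint (section 1.1 and the summary table) is 28-day mortality, counted from first administration "until a patient dies or is followed through 28 days (whichever comes first". Section 7.2 adds "All patients will be followed up for up to 90 days", although it introduces the prospective data with "The following information will be collected prospectively if available".

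Section 9.0 includes "Patient changed to Comfort Care status" among its reasons for stopping the intervention. Section 5.2 excludes "Comfort Care and end-of-life patients" at entry. Section 4.0 describes the trial as un-blinded.

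On analysis, section 10.5 says "Categorical variables, including 28 day mortality, will be compared between intervention groups using a chi-square test", or Fisher's exact test where that suits better. The Brief Analysis Plan in the summary table repeats this. Neither names the patients to be included. Section 10.2 refers to a test after 56 patients are randomised to each arm. Section 10.3 refers to a full analysis set of 112 and an interim look at 28 randomised patients per arm, but does not say who belongs to the set.

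**The concern.** Comfort Care is an exclusion at entry, so a patient who reaches it under 6.4 normally does so after enrolment. The decision is closely tied to impending death and is made by staff who know the treatment arm. If such patients leave the study, some primary-endpoint events may leave with them, through an exclusion that depends on the outcome and arises after randomisation.

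Section 6.4 does not settle its own central case. A patient who moves to Comfort Care and then dies falls under the first sentence (removed) and also under the second (followed up). Two members of staff could record different day-28 data for the same patient, each following the text.

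The analysis plan does not repair this. Nothing in 10.5 says whether a removed patient is left out of the chi-square test or sought for day-28 status. For overall survival, 10.5 follows patients to death or last follow-up, so a removed patient might be censored at removal. That censoring would be informative.

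**Working it through.** **Reading the passages together**

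| Place | What it implies for a patient who reaches Comfort Care in the ICU |
|---|---|
| 6.4, first rule | Leaves the study |
| 6.4, second rule | Followed up, if the patient dies |
| 1.1 and summary table | Followed to death or day 28 |
| 7.2 | Followed, up to 90 days |
| 9.0 | Intervention stops; nothing said on follow-up |
| 10.2, 10.3 | Suggest that all randomised patients count; membership of the set not defined |
| 10.5 and summary table | No population and no rule for removed patients |

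The conflict lies between the first rule of 6.4 on one side and the endpoint definition and 7.2 on the other. Section 7.2 is the weaker of the two, because it sets a maximum and collects data where available.

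**The plan's own figure**

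Inputs from section 10.2: 70% vs 40%, 56 per arm, two-sided alpha 0.05, chi-square test. Pooled rate = 0.55.

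- SE under the null = √(0.55 × 0.45 × 2/56) = 0.0940
- SE under the alternative = √(0.70 × 0.30/56 + 0.40 × 0.60/56) = 0.0896
- Power = Φ((0.30 − 1.96 × 0.0940)/0.0896) = 0.902

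The stated 90% is reproduced. It uses all 56 patients per arm, with no allowance for removal.

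**Illustration: removed patients dropped**

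Let f be the share of 28-day deaths preceded by Comfort Care in the ICU. The documents do not give f, so the values below are assumptions. Every removed patient is assumed to die by day 28, and the interim look is ignored. For true mortality p:

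- observed rate = p(1 − f)/(1 − pf)
- number analysed per arm = 56(1 − pf)

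*Equal f, true 70% vs 40%:*

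| f | Deaths removed, SC / SC + EMR | Analysed, SC / SC + EMR | Observed rates | Power |
|---|---|---|---|---|
| 0 | 0 / 0 | 56 / 56 | 70.0% vs 40.0% | 0.902 |
| 10% | 3.9 / 2.2 | 52.1 / 53.8 | 67.7% vs 37.5% | 0.887 |
| 20% | 7.8 / 4.5 | 48.2 / 51.5 | 65.1% vs 34.8% | 0.869 |
| 40% | 15.7 / 9.0 | 40.3 / 47.0 | 58.3% vs 28.6% | 0.811 |

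For example, at f = 40% the SC rate is 0.70 × 0.60/(1 − 0.28) = 0.583, with 56 × 0.72 = 40.3 patients. The risk difference stays near 30 points, and the cost is power.

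*Unequal f, no true effect (70% in both arms):*

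| f, SC vs SC + EMR | Observed rates | Type I error |
|---|---|---|
| 10% vs 20% | 67.7% vs 65.1% | 0.059 |
| 20% vs 40% | 65.1% vs 58.3% | 0.101 |

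Swapping the arms gives the same totals with the bias reversed. With equal f the type I error stays near 5%.

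**The case against.** The strongest reply is that 6.4 is about adherence, sits in the chapter on interventions, and may mean only removal from study treatment. No passage says that vital status stops being collected or that these patients are left out of the analysis. The second rule of 6.4 can be read to cover a Comfort Care patient who dies, and the references to randomised numbers in 10.2 and 10.3 point towards analysing everyone. All of this is fair, and it means that loss of deaths is a possibility, not a stated plan. It does not remove the problem. 6.4 itself separates leaving the study from stopping the intervention, and places Comfort Care beside requested withdrawal. The phrase in 10.3 may mean only the full 112 as opposed to the interim 56. The consent pages and a figure following 6.4 are not visible here, and either might bear on the question.

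Three stronger readings are tempting but not supported:

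- A reader might infer that section 9.0 contradicts 6.4. It does not. Its list also holds consent withdrawal, death and renal replacement, and it is silent on follow-up, so it neither contradicts 6.4 nor resolves it.
- A reader might count removed patients as survivors, which would give much larger losses of power. No passage supports that handling.
- A reader might infer a bias in favour of EMR. The documents give no sign of a difference in removal between arms, so the direction is unknown.

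**Conclusion.** The point holds. Section 6.4 as written conflicts with the primary endpoint and, less sharply, with the follow-up in 7.2. The statistical section hints at including all randomised patients but does not state it. The point is important because it leaves the handling of primary-endpoint deaths open in an un-blinded trial, not because of the size of the figures.

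On the assumptions shown, the effect is small to moderate. Power of 81% to 89% under equal removal is a limited loss, and a modest imbalance (10% vs 20%) barely moves the type I error. A large imbalance (20% vs 40%) roughly doubles it. These figures rest entirely on assumed values of f, on every removed patient dying by day 28, and on removed patients being dropped.

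**What to change.** 1. Reconcile sections 6.4, 7.2 and 9.0 so that Comfort Care and the other reasons for stopping the intervention do not end vital-status follow-up unless consent to follow-up is itself withdrawn. Clarify in the same way what being withdrawn means in the fluid-overload text of section 8.2.
2. State in section 10.5, and in the Brief Analysis Plan of the summary table, that the primary test and the Cox and log-rank analyses include all randomised patients in their assigned arm, with day-28 status sought for each.
3. Define the full analysis set of section 10.3 in the same words, and say how a patient with unknown day-28 status is handled.

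The rules for stopping treatment are left to the sponsor.

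The cost is a wording amendment with IRB review (section 12.1), and possibly consent wording on keeping vital status after withdrawal. Follow-up to 90 days is already planned, so no new visits are needed. With all 112 patients analysed as randomised, power remains 0.902 and the sample size is unchanged.

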6.5 Required interventions

If the patient does not have a central venous access or arterial line, then this patient cannot be included in the study. All patients treated for septic shock must have central venous and arterial access as standard of care. All participants must have both a central venous catheter and arterial line inserted. As this represents standard of care in septic shock, this is likely to be universal and will not be an impediment to enroll patients.

6.6 Additional fluids to maintain euvoolemia

Additional fluids following sodium algorithm may be required in order to achieve euvoolemia. This should be according to the attending physician's clinical judgement after assessment of the overall hemodynamic parameters and resuscitation status, including pressure (macrocirculation), flow (microcirculation), and function (metabolism). If function is compromised (e.g., rising creatinine, decrease in urine output, rising liver function tests) consider optimizing the coronary and systemic pressure gradient.

Figure 1. Sodium and Albumin to maintain euvoolemia

6.7 Weaning procedure for EMR solution

To wean EMR, decrease rate of both solutions, EMR I or II and Clinisol to half the current rate for 4 hours, and then discontinue. Check serum glucose within 30 minutes of discontinuation of EMR. Further decisions regarding management of IVF, amino acid infusions or parenteral nutrition will be at the discretion of the ICU team or the primary team.

